## **5 OUTCOMES**

### **5.1 Primary outcome**

Reduction of 50% in latent TB in the treatment group after 12 months of intervention, estimated by IGRA QuantiFERON TB Gold Plus – Qiagen.

### **5.2 Secondary outcome**

Reduction of 50% in active TB in the treatment group after 12 months of intervention, estimated by sputum positive culture.

## 6 METHODOLOGY

### 6.1 Study designer

Phase IV, randomized, double-blind, placebo-controlled clinical trial with inmates serving time in a closed regimen.

#### 6.1.1 Sample and population of the study

This research will be carried out at one prison unit, located in the city of Dourados, in the state of Mato Grosso do Sul. Currently, this prison unit has approximately 2,300 inmates, with a mean age of  $31.5 \pm 9.4$  years; an average of  $9.7 (\pm 4.2)$  individuals per cell, who remain in a closed regimen, about  $20.8 (\pm 24.1)$  months. The TB indicators show a tuberculin test seroconversion rate of 26% (23-26) and incidence, 2.45 / 100,000(28).

The sample was calculated for a significance level of 5%, detection power of 90%, considering a percentage of occurrence of latent TB of 20% in the control group after one year of follow-up and 10% in the experimental group. For these parameters, 560 individuals will be needed for the study, however, 30% will be added for possible losses, ending the sample in 728 participants. Memory calculation available at <https://www.sealedenvelope.com/power/binary-superiority/>.

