## 6.6 Estatistical analysis

Data on demographic, socioeconomic, medical and criminal history, as well as on pre, intra and post-intervention laboratory tests will be stored online at REDCap, available at <<http://www.matogrossodosul.fiocruz.br/redcap/>>, where each researcher is identified by single user and password, guaranteeing restricted and confidential access. Statistical analysis will be done with IBM® SPSS Statistics software.

The incidence will be calculated on the basis of the new cases detected during the follow-up period, per 100 person-years. It will be considered a new case of TB individuals, regardless of the group, who present bacilloscopy or positive culture. For latent TB, a seroconversion will be considered for individuals who exhibit interferon gamma levels above the upper limit considered by the manufacturer of the QuantiFERON® TB Gold Plus commercial test in the 12th or 24th month.

The effect of the intervention will be calculated through Relative Risk (RR), considering a Confidence Interval of 95% (95% CI). To determine the effectiveness of the intervention will be used Relative Risk Reduction (RRR) and Absolute Risk Reduction (RAR). In addition, to measure the impact of the intervention, the Number Needed to Treat (NNT) will be calculated.

Two protocols will be performed for statistical analysis: 1) intention-to-treat analysis and 2) per protocol. The sample calculation for the primary outcomes is based on intention-to-treat analysis.

The intent-to-treat analysis will be performed for all subjects who complete at least 6 months of treatment. The participant may decide to withdraw the consent in whole or in part. In the case of withdrawal of partial consent IGRA will be withdrawn at the 12th or 24th month and the participant will remain in the study according to the initial randomization.

Analysis by protocol will be performed only using the group of individuals who completed at least 80% of the predicted doses of the study.

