## 6.7 Interim analysis

After a 6-month visit of at least 100 participants, in addition to the follow-up clinic-laboratorial evaluation (which includes blood collection for hepatic enzyme dosage and directed clinical examination), an evaluation of the effectiveness of the intervention will be carried out, through sputum culture and interferon-gamma dosing / quantification. It is estimated that there is a linear relationship between follow-up time and the risk of acquisition of latent TB.

This evaluation intends to verify the feasibility of continuity of the study and adequacy of the sample calculation. The study will be discontinued if the primary endpoint is less than 2.5% as compared to the control group, or if the difference between the intervention group and the control group is greater than 12.5% according to the box below:

	Intervention (isoniazid) (N=162)	Control (placebo) (N=162)	Finale total number (N final+30%)
Reference	5.0%	10%	726
Insufficient sample	7.5%	10%	3357
Insufficient sample	10.0%	12.5%	3910
Insufficient sample	12.5%	15.0%	4555
Insufficient sample	15.0%	17.5%	5114
Insufficient sample	17.5%	20.0%	5361
Sufficient sample	5.0%	17.5%	172
Sufficient sample	7.5%	20.0%	187
Sufficient sample	10.0%	22.5%	213
Sufficient sample	12.5%	25.0%	218
Sufficient sample	15.0%	27.5%	229

Figura 2 - Sample table of the sample values in both groups (intervention and control), based on the primary outcome.

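### Does adding 30% to 560, giving 728, leave the trial underpowered if 30% of participants are lost?

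*Combined protocol and SAP*

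**What the plan says.** Section 6.1.1 gives the design inputs: "The sample was calculated for a significance level of 5%, detection power of 90"%, with "latent TB of 20% in the control group after one year of follow-up and 10% in the experimental group". It then states that "560 individuals will be needed for the study, however, 30% will be added for possible losses, ending the sample in 728 participants". For the underlying calculation it points to an online calculator for binary superiority trials. It does not name the test, and it does not say whether the 5% is two-sided.

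Section 6.1.2 divides the 728 into two groups of 364. Section 6.6 states: "The effect of the intervention will be calculated through Relative Risk (RR), considering a Confidence Interval of 95% (95% CI"). It limits the analysis it calls intention-to-treat to participants with at least 6 months of treatment, so losses do reduce the analysed number. In section 6.7, the last column of Figure 2 is headed "Finale total number (N final+30"%), which is the same mark-up applied to other scenarios.

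Neither section states the share of randomised participants the sponsor expects to lose.

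**The concern.** The usual way to protect a required number n against a loss fraction d is to randomise n/(1 − d). Multiplying by (1 + d) instead is a common slip, and it always falls short. With n = 560 and d = 0.30, the division gives 800 and the multiplication gives 728, a difference of 72. Since section 6.1.1 says the 30% is for losses, a reader may assume that 728 keeps 560 evaluable after a 30% loss.

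If that were the intention, the trial would finish with about 50 fewer evaluable participants than the number to which the plan attaches 90% power, and every total in the last column of Figure 2 would have the same shortfall. The question is natural in this setting. Participants leave the study on transfer or early release (section 6.4), and time in the closed regimen averages 20.8 months with a standard deviation of 24.1 (section 6.1.1).

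**Working it through.** **Inputs.** Control 20%, isoniazid 10%, significance level 5%, power 90%, required total 560, allowance 30%, final total 728 (section 6.1.1); equal arms of 364 (section 6.1.2). A two-sided test is assumed.

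**The plan's own figures.** 560 × 1.30 = 728, exactly as stated.

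The 560 can be reproduced only approximately, because the test is not named:

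- Pooled normal formula: n per arm = [1.960 × √(2 × 0.15 × 0.85) + 1.282 × √(0.20 × 0.80 + 0.10 × 0.90)]² / 0.10² = 265.9, rounded up to 266; total 532.
- Unpooled normal formula: (1.960 + 1.282)² × 0.25 / 0.01 = 262.7, rounded up to 263; total 526.
- With continuity correction: 286 per arm; total 572.
- Fisher's exact test: 280 per arm gives 89.9% power.

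So 560 lies above the uncorrected formulas and close to the corrected and exact ones. One-sided versions give 430 to 474 and do not fit.

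**Loss that 728 absorbs before falling below 560.** 1 − 560/728 = 1 − 1/1.30 = 0.231. The base number cancels, so the same 23.1% applies to any total formed by a 30% mark-up, including those in Figure 2.

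**A 30% loss.** 728 × 0.70 = 509.6, about 510, or 255 per arm. By the pooled normal approximation:

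- 255 per arm: (0.10 − 1.960 × √(0.255/255)) / √(0.25/255) = 0.03802/0.03131 = 1.214, power 88.8%.
- 280 per arm: (0.10 − 1.960 × √(0.255/280)) / √(0.25/280) = 0.04085/0.02988 = 1.367, power 91.4%.

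The Fisher and relative-risk rows below come from exact enumeration over the two binomial distributions.

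| Method | Power at 560 (23.1% loss) | Power at 510 (30% loss) |
|---|---|---|
| 95% relative-risk interval excluding 1 | 91.6% | 89.0% |
| Pooled normal | 91.4% | 88.8% |
| Unpooled normal | 91.7% | 89.1% |
| Fisher's exact | 89.9% | 86.9% |
| Continuity-corrected normal | 89.4% | 86.2% |

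**Loss at which power reaches 90%.** By the relative-risk interval, 264 per arm gives 90.0% and 263 gives 89.9%. That is 528 in total, and 1 − 528/728 = 27.5%. By the pooled approximation it is 532, and 1 − 532/728 = 26.9%. By Fisher's test or the corrected test, 560 is itself marginally under 90%, so the nominal 90% has no slack even at a 23.1% loss.

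**The case for a change.** The best argument for a change is that attrition matters a great deal here and 30% is the only figure anyone can measure it against. The primary endpoint is at 12 months, inmates may be moved or released, and the analysed set requires at least 6 months of treatment. A team that saw 25% to 30% of participants lost could believe the required 560 was intact when it was not. The interim assessment in section 6.7 also reviews whether the sample is adequate, using a table built with the same mark-up. Stating the allowance as a loss fraction is better reporting and costs one sentence and one column label.

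What stands is the clarity point: 23% is the correct figure for the loss at which 560 remain, and the documents leave the reader to work it out. What does not stand is any suggestion of a wrong number. The section describes an addition and performs it correctly, and Figure 2 labels its column as a mark-up. The shortfall appears only if the reader supplies a 30% loss fraction that the plan never states. Even then, power by the planned relative-risk interval is one point below 90%. The larger gaps depend on tests that the plan does not name. Whether any loss allowance is realistic for this prison is a separate question, which this arithmetic does not address.

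**Conclusion.** The concern does not call for a change. The arithmetic is as described, and no stated sample size or power is shown to be wrong. The missing detail is that a 30% mark-up corresponds to a 23.1% loss of those randomised, and any analyst can derive this from the two totals.

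If 30% were lost, about 510 would be evaluable. Power would be about 89% by the interval planned in section 6.6, or 86% to 87% by Fisher's exact or a continuity-corrected test. Randomising 800 instead would mean 72 more participants and, at that loss, would raise power by the relative-risk interval from 89.0% to 91.6%. That is a small gain against a loss rate the plan does not predict.

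These figures assume 20% versus 10%, a two-sided 5% level, equal arms, and losses that are balanced between arms, unrelated to outcome, and remove the participant from the analysis altogether. A clarifying sentence is optional; the sample size, Figure 2 totals, tests and conclusions would be the same with or without it.

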#### 6.1.2 Randomization and masking

Two groups, called intervention (INH) and control (placebo), respectively, each composed of 364 participants, will be formed from a simple randomization process using the True Random Number Service developed by the School of Computer Science and Statistics in Dublin, Ireland and available at <[www.random.org](http://www.random.org)>. The sequence generator mode used by the principal investigator will produce 728 random alpha-numerical codes, composed of three digits each, that will be delivered to the pharmacist for individual randomization (intervention vs control) containing only the identifying code.

The study pharmacist will be responsible for randomization of the participants and organization of INH-containing bottles or placebo for dispensing during DOT visits. As this is a double-blind study, the other team members are blind and do not have access to the randomization list. The study participants will also not know in which group they are allocated. The description of the pharmacist's activities in the clinical trial are detailed in specific SOP.

The use of placebo was a strategy because there is no clinical trial of primary prophylaxis for TB.

#### 6.1.3 Blinding Break

In the event of any significant AE, the sigil will be broken to identify in which group the participant was allocated. The request for blinding should be made by the study coordinator or lead investigator to the study pharmacist.

In case of breach of blinding, the sponsor must be notified within 48 hours, and the justification for the early breakdown is informed in detail. The reason for the rupture of the blinding should be described in the participant's chart.

At the end of the study randomization will be opened, thus allowing for statistical analysis.

## 6.2 Inclusion criteria

- Age above 18 and under 45 at the time of inclusion;
- Sign the informed consent form.

## 6.3 Exclusion criteria

- Be indigenous;
- Active TB or previous use of INH;
- Sscore AUDIT  $\geq 15$ .
- Reactive serology for HIV, hepatitis B and C;
- Reactive result for IGRA, considering as positive the result of TB1 Tube and / or TB2 Tube above 0.2 IU/mL(53);
- Liver enzymes (AST and ALT) three times the upper limit;
- History or treatment for epilepsy;

## 6.4 Indications for premature exclusion

The participant may be withdrawn from the clinical trial at any time for the reasons listed below:

- at the request of the participant (withdrawal or withdrawal of consent);
- non-compliance with the protocol;
- interruption of treatment or sum of temporary interruptions of intervention  $\geq 90$  days, either by decision of the participant or at medical discretion;
- transfer to another prison unit or early release;
- Clinical or laboratory AE requiring permanent discontinuation of medication (according to study-specific SOP);
- any exclusion criterion according to item 5.3 that, incidentally, arises during the follow-up (both recently diagnosed and not previously recognized);
- use of acetaminophen, valproic acid, carbamazepine, cycloserine, ethionamide, corticosteroids, diazepam, triazolam, disulfiram, phenytoin, aluminum hydroxide and rifampicin which, at the discretion of the investigator, are used in a dose that may interfere with the efficacy of INH as medication;
- another reason, at the discretion of the principal investigator or study coordinator.

At the time of the participant's withdrawal, a premature exclusion visit with clinical evaluation, evaluation of AE and blood and / or sputum collection should be performed according to the clinical judgment, according to the study schedule (figure 1).

In addition, for cases in which treatment has been interrupted by decision of the participant or at medical discretion, as of 6 months from the start of the DOT, the participant will have two options: to remain in the study without the intervention (DOT), but with the accomplishment of all the visits anticipated in the protocol or to leave completely of the study without the realization of

additional collections and other accompaniments. For the latter case, follow-ups will be carried out only if the participant presents some AE at the time of their withdrawal.

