## **2.3 The relation prison and tuberculosis**

The world prison population is currently estimated at 10.2 million people(24). Brazil has the third largest population in the world, with 688,759 individuals in 1,449 establishments, and the incidence of TB in this population has increased in the last seven years(25). Although prisoners represent only 0.3% of the country's population, an increase in the prison population over this period has resulted in almost double the proportion of all TB cases among prisoners (4.1% in 2007, 8% 1% in 2013).

The prison environment contributes greatly to the transmission of TB. Prisons are an ideal environment for the transmission of the disease, since they bring together individuals who use tobacco and alcohol in high doses, in addition to drug abuse, in overcrowded cells, with little ventilation and with limited access to care. health and diagnosis of TB. Urrego et al.(26) collected architectural and ventilation data in a southern prison in Mato Grosso do Sul and, using a modified Wells-Riley model for indoor TB transmission, projected TB transmission rates within each cell , provided that an infectious case was present. They estimated that 53-70% of cell mates would be infected after four months of exposure.

In a case-control study associated with molecular methods, Sacchi and cols.(27) examined the role of prison in TB burden in the population of Dourados. Among 240 cases of TB reported over a 46-month period, 180 (75%) occurred in the general population and 60 (25%) in the prison population, showing a 40-fold increased risk (incidence) among prisoners of TB. Among the TB cases of the general population, 23% occurred among residents who were previously incarcerated. Previous incarceration was the strongest risk factor for TB in the community (adjusted OR, 28.5). Among 97 isolates for which restriction fragment polymorphism (IS6110) genotyping was performed, 79 could be classified into 17 groups. Ten of these 17 sets, comprising 82% of the clustered isolates, involved two prisoners and community members, including the former detainees. These results demonstrate a high degree of linkage between lineages in prisons and in the community; and indicate that the approach to TB transmission in prisons will be critical to disease control among the general population.

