At follow-up visits of 6, 12 and 24 months, if the interferon gamma result is indeterminate, the participant remains in the clinical trial and a new sample is collected within 30 days. If the IGRA result is positive (result standardized according to the package insert of the Qiagen®), the participant will suspend the medication (in the case of the 6-month visit), will be excluded from the study and treatment for latent TB.

If the sputum culture is positive for Mtb, the participant will be excluded from the study and treatment for active TB according to MS will be offered. If the sputum culture is contaminated, a new sample should be collected within 30 days after the result.

In the occurrence of hepatotoxicity, diagnosed through hepatic enzyme levels (elevation greater than five times the upper limit of the test if the individual is asymptomatic) and / or clinical examination (presence of jaundice, right upper quadrant pain, dark urine, fever, asthenia, myalgia), the intervention will be interrupted and the participant will be led to clinical care by the project team, according to the project's SOP. In this study, the following values will be used as laboratory parameter: AST: 8-40 IU / mL and ALT: 5-30 IU / mL(54,55). Other laboratory tests may be

requested from the research participants, according to the clinical judgment of the physician responsible for the care of the AE and according to the specific SOP of the project.

IGRA, smear culture, and serology for HIV, hepatitis B and C are performed LPCS / UFGD. The AST/ALT exams and other laboratory tests, when necessary, are performed in an external laboratory.

During the course of the study, the Notification of Injury Information System will be used to identify the occurrence of active TB cases in both groups.

The box below summarizes the activities to be developed at each stage of the protocol.

	Enrollment	DOT start (D0)	1 st visit (3 mo± 15 d)	2 nd visit (6 mo± 15 d)	3 rd visit (9 mo± 15 d)	4 th visit (12 mo± 30 d)	5 th visit (24 mo± 30 d)	Early exclusion visit
Consent process	X							
Verification of inclusion and exclusion criteria	X							
AUDIT	X							
Medical history	X							
Criminal history	X							
Randomization		X						
DOT star		X						
DOT end						X		
IGRA	X			X		X	X	(X)
ALT, AST	X		X	X	X	X		(X)
Another laboratory exams	(X)		(X)	(X)	(X)	(X)		(X)
Anti-HIV, HBsAg e Anti-HCV	X							(X)
Sputum coleccion	X			X		X	X	(X)

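### The plan does not say that follow-up for active TB through the notification system continues after a participant is transferred or released, so active-TB cases arising after exit can be dropped

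*Combined protocol and SAP*

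**What the plan says.** - **Section 6.4** opens its list with "The participant may be withdrawn from the clinical trial at any time for the reasons listed below", and one listed reason is "transfer to another prison unit or early release". The withdrawal is from the trial, not only from dosing. A premature exclusion visit is provided, with blood and sputum collection left to clinical judgement.
- The same section offers an off-treatment option, "to remain in the study without the intervention (DOT), but with the accomplishment of all the visits anticipated in the protocol". It applies only when treatment was interrupted by the participant's or a medical decision, from month 6. Transfer and release are not covered.
- **Figure 1** schedules nothing after the early exclusion visit.
- **Section 6.5** says that, while the study runs, "the Notification of Injury Information System will be used to identify the occurrence of active TB cases in both groups". It does not say whether this includes people who have left.
- **Section 6.6** bases incidence on "new cases detected during the follow-up period, per 100 person-years" but does not define when that period ends for someone withdrawn. It restricts the set called intention-to-treat to those with at least 6 months of treatment.
- **Section 5.2** defines the only secondary outcome as "Reduction of 50% in active TB in the treatment group after 12 months of intervention, estimated by sputum positive culture". Section 6.6 counts people "who present bacilloscopy or positive culture".
- **Section 4.2** includes active-TB incidence, and residual protection up to a year after the intervention, among the specific aims.

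**The concern.** Leaving the prison makes supervised dosing and IGRA sampling hard. It does not by itself prevent a search of notification records. If exit also ends the search, the trial gives up events on a rare outcome that it could recover at little cost.

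Exit will be common. Section 1 says inmates usually leave within one to two years, section 6.1.1 gives a mean of 20.8 months in the closed regimen, and follow-up runs 24 months from D0. Disease in former inmates is a known part of the local epidemic: "Among the TB cases of the general population, 23% occurred among residents who were previously incarcerated" (section 2.3).

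Precision is not the only issue. Without a rule, whether a case notified after exit counts can be decided one case at a time. The 6-month treatment condition in 6.6 also selects participants on something that happens after randomisation. It would keep early leavers out of the main analysis even if their records were searched.

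**Working it through.** **The plan's own figures.** The plan gives no event count, sample size or power for active TB. Its 560 is for latent TB (20% v 10%, 5% level, 90% power). A two-sided test of two proportions with continuity correction gives 286 per arm, 572 in total, within 3% of 560. The final size is 560 × 1.30 = 728.

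**Person-time if everyone is followed.** 728 × 1 year = 728 person-years (PY) to month 12, and 728 × 2 = 1,456 PY to month 24.

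**Person-time if follow-up stops at exit.** With S(t) the proportion still in the prison unit at month t, mean observed time to T is the integral of S(t) from 0 to T. The documents do not give S(t), so four assumed patterns follow.

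- A: exponential, mean 20.8 months taken as time remaining from D0. Mean observed time is 20.8 × (1 − exp(−T/20.8)): 9.1 months for T = 12 and 14.2 months for T = 24.
- B: lognormal with mean 20.8 and SD 24.1 (section 6.1.1), also as time remaining from D0.
- C: constant hazard, 30% gone by month 12, S(t) = 0.7^(t/12).
- D: constant hazard, 30% gone by month 24, S(t) = 0.7^(t/24).

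| Pattern | Still in at 6 / 12 / 24 months | PY lost to month 12 | PY lost to month 24 | Lost to month 24 with the 6-month rule |
|---|---|---|---|---|
| A | 75% / 56% / 32% | 175 (24%) | 592 (41%) | 44% |
| B | 81% / 55% / 27% | 142 (19.5%) | 585 (40%) | 43% |
| C | 84% / 70% / 49% | 116 (16%) | 415 (28.5%) | 30% |
| D | 92% / 84% / 70% | 61 (8%) | 231 (16%) | 17% |

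Complete follow-up would therefore give 1.09 to 1.32 times the person-time to month 12, and 1.19 to 1.69 times to month 24. Under pattern A, 1 − exp(−6/20.8) = 25% leave before month 6 and fall outside the 6-month set.

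Patterns C and D read the allowance as 30% lost. Adding 30% to 560 strictly leaves room for 168/728 = 23% lost. With S(t) = (560/728)^(t/24), pattern D would fall to about 6% and 12%.

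**Events and power to month 24.** The printed incidence of 2.45 per 100,000 would give 1,456 × 0.0000245 = 0.04 events, so it cannot be used as it stands. I assume 2.45 per 100 PY in controls. Section 2.3 gives a similar rate: prevalence 917 per 100,000 divided by 4.8/12 year is about 2,290 per 100,000 per year. With a hazard ratio of 0.5, the average rate over both arms is 0.75 of the control rate.

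- Complete follow-up: 1,456 × 0.0245 × 0.75 = 26.8 events. By Schoenfeld's formula, two-sided 5%, z = √26.8/2 × ln 2 − 1.96 = −0.17, so power is about 43%.
- Follow-up stopping at exit: 15.9 (pattern A) to 22.5 events (pattern D), power about 28% to 38%.
- Needed: 66 events for 80% power, 88 for 90%.

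These event counts assume the same TB rate before and after exit. The gain is smaller if risk falls after release.

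**The case against.** A reader might infer that the plan withdraws everyone who leaves and discards their later person-time. The text does not go that far. Section 6.4 says participants may be withdrawn, so withdrawal is permitted, not automatic. Section 6.6 does not say that the follow-up period ends at withdrawal. Section 6.5 speaks of both groups without excepting leavers, and could already cover everyone randomised. What stands is that the plan is silent, and one reading of it drops these cases.

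A reader might also take the top ratios, 1.32 and 1.69, as the size of the gain. They hold only if exit is exponential and 20.8 months is time remaining after D0, which section 6.1.1 does not establish. The larger one concerns month 24, whereas the secondary outcome is defined at 12 months.

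Nor do the community figures in section 2.3 (23% of cases; adjusted odds ratio 28.5 for previous incarceration) predict the yield here. They describe cases in the general population, not incidence after release in a cohort that is IGRA-negative at entry.

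Three further objections stand in part. The documents do not say that the system covers other prisons or the community, can be linked to participants, or records smear or culture results. The general aim concerns inmates in a closed regimen, so adding time off drug and out of prison may dilute the contrast; this is partly a choice of estimand. And power stays low either way. These call for conditions and a sensitivity analysis. They do not justify leaving the rule unstated.

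**Conclusion.** The point holds as a gap in the plan: transfer and early release are grounds for withdrawal from the trial, no off-treatment follow-up is offered to those who leave this way, and nothing says that the planned search or the person-time continues for them.

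If follow-up stops at exit, about 8–24% of person-time is lost over 12 months and 16–41% over 24 months (17–44% with the 6-month rule). The 12-month loss is moderate. The 24-month loss is large if the stated mean stay describes time remaining. These are scenarios, not bounds: they rest on assumed exit patterns, and the 30% allowance covers all losses, not only transfer and release.

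The documents do not support the stronger conclusion that these data will be discarded. The change should be made all the same, because it settles the question on either reading.

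**What to change.** 1. **Section 6.4.** State that transfer or release ends supervised dosing and study visits, as withdrawal already would, but not passive follow-up for active TB.
2. **Sections 6.5 and 6.6.** State that the notification system is searched, blinded to arm, for every randomised participant to month 24 from D0, subject to consent and system coverage. Describe that coverage. Count person-time from D0 on the same basis.
3. **Case definition.** Count a notified case only if it meets the smear or culture definition in 6.6. Put other notified cases in a sensitivity analysis.
4. **Analysis.** Analyse active TB by randomised arm in all randomised participants, without the 6-month treatment condition. Report months 0–12 and 0–24, with a sensitivity analysis censored at exit. Say how participants whose pre-dose culture later proves positive are handled, since they had disease at entry.

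The cost is protocol wording, a blinded record search and possibly consent wording; the consent pages were not available, so whether those need changing cannot be judged. Some post-exit cases will be missed or lack bacteriological confirmation, and time off drug and out of prison may dilute the effect. Active TB stays underpowered. The primary IGRA outcome, which needs a blood sample, is not helped.
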